dose adjustment is necessary when co-administering ruxolitinib with CYP3A4 substrates. Ruxolitinib did not decrease the exposure of a fixed dose oral contraceptive metabolized via the CYP3A4 pathway, thus demonstrating lack of CYP3A4 induction potential.

In patients with severe renal impairment [creatinine clearance (Cl_{cr}) < 30 mL/min], the recommended starting dose based on platelet count should be reduced by approximately 50% to be administered twice a day. Patients on hemodialysis should initiate ruxolitinib with a single dose of 15 mg or 20 mg (or two doses of 10 mg given 12 hour apart) based on platelet counts on day of hemodialysis with subsequent doses only on hemodialysis days and following each hemodialysis session. Ruxolitinib doses should be titrated based on individual safety and efficacy.

In patients with mild, moderate or severe hepatic impairment, the recommended starting dose based on platelet count should be reduced by approximately 50% with subsequent dose titration based on individual safety and efficacy.

Ruxolitinib PK in healthy volunteers was largely comparable between Japanese, Chinese and Western subjects and did not lead to a conclusion of meaningful ethnic differences.

[figure not shown]
Baseline elevations in inflammatory markers such as tumor necrosis factor alpha (TNF α), interleukin (IL)-6, and C-reactive protein (CRP) noted in patients with MF were associated with constitutional symptoms such as fatigue, pruritus, and night sweats. Decreases were observed in these markers over the 24 weeks of treatment with ruxolitinib, with no evidence that patients became refractory to the effects of ruxolitinib treatment.

Please refer to the [Investigator Brochure] for additional details on pharmacokinetics and pharmacodynamics.

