4.1 Description of study design

This is a double blind, randomized placebo-controlled study of ruxolitinib in patients with HMR positive early MF (HMR+ EMF). The study consists of a screening period, Treatment Period 1 and Treatment Period 2.

Screening:

Patients will be pre-screened for the determination of HMR mutation status after obtaining the molecular pre-screening informed consent. Only patients who are centrally confirmed to be HMR+ will be eligible to enter the screening phase. Patients should be consented to the main study informed consent as soon as HMR positivity is confirmed (recommended within 28 days). Patients will be randomized in a 1:1 ratio to ruxolitinib or placebo on Day 1 following confirmation of eligibility, including confirmed bone marrow fibrosis grading during the 40 day screening period.

Treatment Period 1

[figure not shown]
Blinded study treatment will begin on Day 1 following randomization. Visits will be every 4 weeks up to Week 24 to monitor tolerability and efficacy with the study treatment. After Week 24, visits will be every 8 weeks until Week 48, and then every 12 weeks thereafter. Blinded study treatment will be administered until disease progression or patient discontinuation. A 30-day safety follow up visit will be done after the last dose of blinded study drug (except if entering Treatment Period 2). Patients who discontinue for reasons other than disease progression will enter the post treatment follow up. Patients will be followed for survival after end of Treatment Period 1 or post-treatment follow up every 3 months until the termination of study by the sponsor.

Treatment Period 2

[figure not shown]
Patients who progress due to splenomegaly or symptoms and are candidates for treatment with currently approved doses of ruxolitinib (as per investigators decision) will be treated with ruxolitinib at 5mg, 15mg or 20 mg BID, based on platelet counts at the time of treatment initiation ([Section 6.1](#)). These patients will continue on the same schedule of assessments as in 'Treatment Period 1' ([Table 7-1](#)). A 30-day safety follow up visit will be performed after the last dose of study drug. Patients will be followed for survival after end of Treatment Period 2 every 3 months until the termination of study by the sponsor ([Figure 4-1](#)).

Figure 4-1 Schematic study design

A) Screening

B) Treatment Period

[figure not shown]

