5.3 Exclusion criteria

Patients eligible for this study must not meet **any** of the following criteria at screening:

1. Patients with prior treatment with ruxolitinib or other JAK inhibitors.
2. Patients with known hypersensitivity to ruxolitinib or any of its excipients.
3. Patients with inadequate liver function defined by any of these:
Total bilirubin $\geq 2.5 \times \text{ULN}$ and subsequent determination of direct bilirubin $\geq 2.5 \times \text{ULN}$;
Alanine aminotransferase (ALT) $> 2.5 \times \text{ULN}$; Aspartate aminotransferase (AST) $> 2.5 \times \text{ULN}$.
4. Patients with severely impaired renal function defined by:
Serum creatinine $> 2 \text{ mg/dL}$.
5. Patients with active bacterial, fungal, parasitic, or viral infection which requires therapy.
6. Impairment of gastrointestinal (GI) function or GI disease that may significantly alter the absorption of ruxolitinib (e.g., ulcerative diseases, uncontrolled nausea, vomiting, diarrhea, malabsorption syndrome, small bowel resection).
7. Known history of human immunodeficiency virus (HIV) infection or other immunodeficiency syndromes such as X-linked agammaglobulinemia and common variable immune deficiency.
8. Active hepatitis A, B or C infection, which requires treatment.
9. History of progressive multifocal leuko-encephalopathy (PML).
10. History or current diagnosis of uncontrolled or significant cardiac disease, including any of the following:
 - Myocardial infarction within last 6 months
 - Uncontrolled congestive heart failure
 - Unstable angina within last 6 months
 - Clinically significant (symptomatic) cardiac arrhythmias (e.g., sustained ventricular tachycardia, and clinically significant second or third degree AV block without a pacemaker)

11. Significant concurrent, uncontrolled medical condition, which in the investigator's opinion would jeopardize the safety of the patient or compliance with the protocol.
12. Patients being treated concurrently with a strong (potent) systemic inhibitor or inducer of CYP3A4 ([Appendix 1](#)) at the time of Screening.
13. Patients under ongoing treatment with another investigational medication or having been treated with an investigational medication within 30 days or 5 half-lives (whichever is longer) prior to the first dose of study treatment.
14. Patients with a history of malignancy in the past 3 years, except for well-controlled early stage squamous or basal cell carcinoma in situ.
15. Patients eligible for stem cell transplantation.

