6.1 Study treatment

Treatment Period 1:

The study treatment will consist of INC424 (ruxolitinib) or matching placebo administered in a blinded manner following randomization of the patient on study Day 1.

Treatment Period 2:

INC424 (ruxolitinib) administered as per [Table 6-1](#).

Table 6-1 Starting Doses of INC424 based on platelet counts (Treatment Period 2)

INC424	Platelet count (x 10 ⁹ /L)
5 mg BID	50 – <100
15 mg BID	100 – 200
20 mg BID	>200

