6.1.1 Dosing regimen

Table 6-2 Dose and treatment schedule

Treatment Period 1 (INC424/Placebo - Blinded)

Study treatments	Pharmaceutical form and route of administration	Dose	Frequency and/or Regimen
INC424/ Placebo	Tablet for oral use	10 mg BID (2 tablets of INC424 5mg/placebo BID)	Daily

Study treatment will be administered orally twice per day at a dose of 10 mg BID, given as 2 tablets of INC424 5mg / placebo ([Table 6-2](#)). Study treatment should be taken orally twice daily, approximately 12 hours apart (morning and night) without regards to food. Study treatment will be self-administered by the patient in an outpatient setting, and each investigator should instruct the patient to take the study drug as per protocol. All dosages taken by the patient must be recorded on the Dosage Administration Record case report form (CRF).

Patients should be instructed not to take study treatment at Week 12, Week 24 and Week 48 visit (and every 12 weeks thereafter) on the day of the scheduled pre-dose blood collection ([Section 7](#)). Dosing will be administered post blood collection at these visits.

Treatment Period 2 (INC424)

Once the patient progresses in Treatment Period 1 by splenomegaly or symptoms, the patient will start treatment with INC424 (ruxolitinib) 5/15/20 mg BID based on platelet count as per approved label ([Table 6-1](#) and [Table 6-3](#)).

Table 6-3 Dose and treatment schedule

Treatment Period 2 (INC424)

Study treatments	Pharmaceutical form and route of administration	Dose	Frequency and/or Regimen
INC424	Tablet for oral use	5/15/20 mg BID	Daily

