6.3 Dose modifications

6.3.1 Dose modification and dose delay

6.3.1.1 Dose modification for hematologic toxicity

Treatment Period 1

Dose reductions or interruptions for hematological changes are permitted in order to allow the patient to continue on the study treatment. The maximum allowed doses for different ranges of cytopenia is described in [Table 6-4](#). The objective of the dose adjustment rules is to optimize treatment response for each individual patient while avoiding significant cytopenia. Dosing may be restarted or increased following recovery of the hematologic parameter(s) to acceptable levels. Any patient requiring dose interruption continuously for more than 4 weeks

due to decreases in ANC or platelet (PLT) counts must be permanently discontinued from treatment. Hb levels decreasing below 8g/dL with an absolute drop of 3g/dL from baseline, will constitute a marker of progressive MF disease, if Hb levels fail to recover \geq 8g/dL following treatment interruption for two consecutive weeks. Such patients must permanently discontinue study treatment.

Table 6-4 Dose reductions and interruptions due to hematological changes – Treatment Period 1

Current Hb (g/dL)	Maximum allowable dose
< 8	Interrupt dosing (HOLD)
8 to < 10	Reduce total daily dose to 5 mg BID
Current PLT ($\times 10^9/L$)	
< 50	Interrupt dosing (HOLD)
50 to < 75	Reduce total daily dose to 5 mg BID
Current ANC ($\times 10^9/L$)	
< 0.5	Interrupt dosing (HOLD)
0.5 to < 0.75	Reduce total daily dose to 5 mg BID

All dose changes must be recorded on the Dosage Administration Record CRF.

Patients whose dose has been interrupted for more than 4 weeks for any reason are recommended to be permanently discontinued from study treatment.

Treatment Period 2

Dose reductions and interruptions for ruxolitinib treatment during ‘Treatment Period 2’ can be performed in accordance with the local label requirements. In countries where ruxolitinib is not currently approved, treatment should be discontinued for platelet counts less than $50 \times 10^9/L$ or absolute neutrophil counts less than $0.5 \times 10^9/L$. After recovery of blood counts above these levels, dosing may be re-started at 5 mg twice daily and gradually increased based on careful monitoring of complete blood cell count, including a white blood cell count differential.

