6.3.1.2 Dose modification for non-hematological toxicity (Treatment Period 1 and 2)

Study drug MUST be permanently discontinued upon the occurrence of a clinically significant Grade 3 or Grade 4 laboratory or non-laboratory abnormality attributed to ruxolitinib if it fails to resolve to Grade 2 or better within 8 weeks or if a lower re-start dose or administration schedule is either not available or likely to be clinically ineffective. Specific recommendations that are to be followed in the event of abnormal liver function tests are provided in [Table 6-5](#).

[figure not shown]
[figure not shown]
[figure not shown]

Table 6-5 Dose modifications for abnormal liver function tests

Isolated Elevation of Total Bilirubin	
> ULN – 1.5 x ULN	Maintain dose level
>1.5x baseline AND > 1.5 - 3.0 x ULN	Omit dose with weekly monitoring of LFTs ^a , or more frequently if clinically indicated, until resolved to ≤ 1.5 x ULN or baseline levels - If resolved in ≤ 14 days, then maintain dose level - If resolved in > 14 days, then ↓ 1 dose level ^d
> 3.0 - 10.0 x ULN	Omit dose with weekly monitoring of LFTs ^a , or more frequently if clinically indicated, until resolved to ≤ 1.5 x ULN or baseline levels - If resolved in ≤ 14 days, then ↓ 1 dose level ^d - If resolved > 14 days, discontinue patient from study drug treatment. The patient should be monitored weekly (including LFTs ^a), or more frequently if clinically indicated, until total bilirubin have resolved to baseline levels or have remained stable over 4 weeks.
> 10.0 x ULN	Discontinue patient from study drug treatment. The patient should be monitored weekly (including LFTs ^a), or more frequently if clinically indicated, until total bilirubin have resolved to baseline levels or have remained stable over 4 weeks.

Isolated AST or ALT elevation	
> ULN - 3.0 x ULN	Maintain dose level
> 3.0 - 5.0 x ULN	Maintain dose level. Repeat LFTs ^a as soon as possible, preferably within 48-72 hours from awareness of the abnormal results; if abnormal lab values are confirmed upon the repeat test, then monitor LFTs ^a weekly, or more frequently if clinically indicated, until resolved to ≤ 3.0 x ULN
> 5.0 - 10.0 x ULN	Omit dose. Repeat LFTs ^b as soon as possible, preferably within 48-72 hours from awareness of the abnormal results; monitor LFTs ^b weekly, or more frequently if clinically indicated, until resolved to ≤ 3.0 x ULN Then - If resolved in ≤ 14 days, maintain dose level - If resolved in > 14 days, ↓ 1 dose level

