6.5.2 Treatment assignment or randomization

Treatment Period 1

Patients will be assigned to one of the “2” treatment arms ([Section 4.1](#) and [Section 6.1](#)) in a ratio of 1:1 (ruxolitinib or placebo).

The randomization numbers will be generated using the following procedure to ensure that treatment assignment is unbiased and concealed from patients and investigator staff. A patient randomization list will be produced by the IRT provider using a validated system that automates the random assignment of patient numbers to randomization numbers. These randomization numbers are linked to the different treatment arms, which in turn are linked to medication numbers.

Prior to dosing, all patients who fulfill all inclusion/exclusion criteria will be randomized via IRT to one of the treatment arms. The investigator or his/her delegate will log on to the IRT and confirm that the patient fulfills all the inclusion/exclusion criteria. The IRT will assign a randomization number to the patient, which will be used to link the patient to a treatment arm and will specify a unique medication number for the first package of study treatment to be dispensed to the patient. The randomization number will not be communicated to the caller.

Treatment Period 2

Patients entering Treatment Period 2 will be assigned to receive ruxolitinib by the IRT. Sites must enter all required information including dosage (5/15/20 mg) in the IRT to ensure ruxolitinib medication assignment.

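### Treatment Period 2 starting doses are set by platelet count alone, without the roughly 50% hepatic reduction that the protocol's own pharmacology summary recommends

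*Protocol*

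**What the plan says.** **Background.** Protocol Section 1.2.1.2.1 says: "In patients with mild, moderate or severe hepatic impairment, the recommended starting dose based on platelet count should be reduced by approximately 50" per cent, followed by titration on individual safety and efficacy. The same section recommends about a 50% cut in total daily dose with strong CYP3A4 inhibitors.

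**Period 2 starting dose.** Table 6-1 is titled "Starting Doses of INC424 based on platelet counts (Treatment Period 2") and lists 5 mg BID (platelets 50 to <100 × 10⁹/L), 15 mg BID (100–200) and 20 mg BID (>200). Section 6.1.1 repeats "5/15/20 mg BID based on platelet count as per approved label". Section 6.5.2 adds: "Sites must enter all required information including dosage (5/15/20 mg) in the IRT". Under Section 4.1, Period 2 is for patients who progress by spleen or symptoms and are "candidates for treatment with currently approved doses of ruxolitinib (as per investigators decision"). No liver criterion is named at that step.

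**Liver rules elsewhere.**
- Exclusion criterion 3 applies at screening. It removes ALT or AST above 2.5 × ULN, and total bilirubin of at least 2.5 × ULN "and subsequent determination of direct bilirubin" at the same level.
- Section 6.3.1.2 covers both periods: "Specific recommendations that are to be followed in the event of abnormal liver function tests are provided in" Table 6-5.
- Section 6.3.1.1 lets Period 2 reductions and interruptions follow the local label, then says: "In countries where ruxolitinib is not currently approved, treatment should be discontinued for platelet counts less than" a stated level, with a matching neutrophil limit. It gives no liver rule.

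**The concern.** The pharmacology section makes two recommendations of the same size: about half the dose with strong CYP3A4 inhibitors, and about half the platelet-based start in hepatic impairment. The first became mandatory in Section 6.4.2. The second does not appear in Section 6, and no reason is given. A site that doses from Table 6-1 has nothing there to prompt a reduction.

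What is at stake is patient safety in Period 2. Section 1.2.1.2.1 reports dose-proportional exposure from 5 to 200 mg, so doubling the dose roughly doubles exposure in a given patient. Section 1.2.1.2.3 describes anemia, thrombocytopenia and neutropenia as dose related.

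**Working it through.** The plan states no figure to reproduce on this point. The check is a dose ratio, followed by a reading of which existing rules could catch the patient.

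**1. Dose ratio.** Inputs are the Table 6-1 doses, the 50% reduction in Section 1.2.1.2.1, and Table 6-5 footnote d (one dose level is 10 mg per day).

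- Written daily dose = 2 × BID dose.
- Recommended daily dose = written × (1 − 0.50).
- Ratio = written ÷ recommended.
- Dose after one Table 6-5 step = written − 10 mg.

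| Platelets (× 10⁹/L) | Written, mg/day | Halved, mg/day | Ratio | After one step, mg/day | Step ÷ halved |
|---|---|---|---|---|---|
| 50 to <100 | 10 | 5 | 2.0 | 0 | 0 |
| 100–200 | 30 | 15 | 2.0 | 20 | 1.33 |
| >200 | 40 | 20 | 2.0 | 30 | 1.5 |

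The recommendation is only approximate. If it is taken as a 40–60% cut (an assumption), the ratio runs from 1 ÷ 0.6 = 1.67 to 1 ÷ 0.4 = 2.5.

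**2. Who passes the liver rules.** Take total bilirubin stable at 2.0 × ULN, chosen only to test the rules.

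- Exclusion criterion 3: 2.0 is below 2.5, so the patient is eligible on bilirubin.
- The first action row for isolated bilirubin in Table 6-5 needs a value above 1.5 × baseline and between 1.5 and 3.0 × ULN. Here 1.5 × 2.0 = 3.0, so a stable value does not trigger it.
- The next row starts above 3.0 × ULN whatever the baseline, so it is not reached either.

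A patient whose bilirubin rises newly above both 1.5 × ULN and 1.5 × baseline is caught: the dose is omitted and liver tests are repeated weekly. The gap is therefore mainly stable, pre-existing impairment below the exclusion limits.

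**3. How soon blood counts would show a problem.** Section 7.1.4 says the Period 2 schedule carries on from the point reached in Period 1, and SAP Section 2.1.10 applies the same imaging windows across periods. On that reading, a patient entering Period 2 after Week 48 has scheduled hematology every 12 weeks. Week 48 is 336 ÷ 30.4375 = 11.04 months. With the design's exponential 50-month control median (Section 10.8), the control fraction still progression-free then is exp(−ln 2 × 11.04 ÷ 50) = 0.858. Late entry to Period 2 is thus an ordinary case. Table 7-1 part B could also be read as restarting at Week 4, which would give 4-weekly counts at first.

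**The case against.** Several points against this are sound.

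- **Background is not an instruction.** Section 1.2.1.2.1 is a pharmacology summary that refers to the Investigator's Brochure. The operative text ties Period 2 to approved doses and the label, and leaves candidacy to the investigator. A reader might infer that the protocol directs every hepatically impaired patient to a double dose. The documents do not support that: where the drug is approved (over 90 countries, Section 1.2.1), the label or the investigator may supply the reduction. The label text is not available here, and the documents do not list the site countries. What remains is that Section 6.1.1 attaches the label to the platelet-based doses, the local-label sentence in Section 6.3.1.1 concerns reductions and interruptions, and neither states a hepatic start.
- **The IRT list.** A reader might infer that sites could not enter a halved dose. Section 6.5.2 asks for all required information including dosage, which is not an exclusive list, and Section 6.4.2 and Table 6-5 already lead to other Period 2 doses. The list shows only that no halved dose is named.
- **Table 6-5 does protect.** It covers new bilirubin rises in both periods, so the exposed group is narrower than all hepatic impairment.
- **The bilirubin example.** An isolated total bilirubin of 2.0 × ULN need not be hepatic impairment, and the documents define no grades. The example shows where the rules stop, not who is impaired.
- **Period 1.** A reader might extend the argument to the fixed 10 mg BID dose. The hepatic recommendation is a fraction of a platelet-based start. Period 1 uses one fixed dose with its own rationale in Section 2.3, so the mismatch shown here does not carry over.

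**Conclusion.** The point holds as a minor safety correction. The protocol's pharmacology summary recommends about half the platelet-based start in mild, moderate or severe hepatic impairment. The Period 2 dosing text omits this, and a literal reading gives 2.0 times the recommended dose in each tier (1.67 to 2.5 if the cut is 40–60%).

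This assumes that the site doses from Table 6-1 without drawing a reduction from the label or Investigator's Brochure, and that the impairment is stable and below the exclusion limits. The gap is clearest where ruxolitinib is not approved. Routine blood counts cannot be relied on to contain the risk early, because they may be 12-weekly.

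A reader might also infer a threat to the trial's conclusions. There is none: no endpoint, sample size, power or analysis depends on this. SAP Section 2.8 keeps Period 2 data, other than deaths, out of the safety summaries. SAP Sections 1 and 1.2 record early termination with minimal enrolment.

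**What to change.** Add one rule to Section 6.1 and Table 6-1. Patients with hepatic impairment (mild, moderate or severe) would start Period 2 at about 50% of the Table 6-1 daily dose and then be titrated. Where halving the BID dose is impractical, use once-daily dosing, as Section 6.4.2 already allows:

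- platelets >200: 10 mg BID;
- 100–200: 15 mg once daily;
- 50 to <100: 5 mg once daily.

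Take the definition of impairment from the label or Investigator's Brochure, judged on medical history and the End of Treatment Period 1 chemistry. A single cut-off such as total bilirubin >1.5 × ULN would not do: it misses some mild impairment that the recommendation covers and can capture isolated indirect bilirubin elevation. Confirm that the IRT accepts the reduced doses. Leave Period 1 dosing as it is.

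The cost is a short amendment, an IRT check and an agreed definition. No new test is needed: ALT, AST, albumin and total bilirubin are already measured at end of treatment (Section 7.2.2.5.2), and those assessments fall within 2 weeks before the first Period 2 dose (Section 7.1.4). With 5 mg tablets, as used in Period 1, the doses need 20 ÷ 5 = 4, 15 ÷ 5 = 3 and 5 ÷ 5 = 1 tablet per day; Period 2 tablet strengths are not stated. The downsides are that some patients will start lower than they need, and once-daily dosing in the two lower tiers halves the daily total but not the single dose. With the trial closed, the change is for a restart or a similar protocol.
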